#### 3.1.1 Definition of Baseline and Study Day for Analysis Purposes

In general, baseline will be defined as the last non-missing valid observation prior to the first administration of investigational product (IP). In cases where measurements are taken on the same day as the first administration of IP and no time is reported, it will be assumed that these measurements are taken prior to the first administration of IP. Missing baseline evaluations will not be imputed and will be considered as missing.

Table 2 provides definition of baseline and study reference days for reporting purposes.

	RCP	OLP	Combined RCP and OLP (for Any Inebilizumab Exposed Analysis)	SFP
Baseline*	The last non-missing valid observation prior to the first administration of IP.	The last non-missing valid observation prior to the 1 st administration of IP during OLP.	The last non-missing valid observation prior to the first administration of inebilizumab (i.e., first RCP dose in those randomized to active drug, first OLP dose in those randomized to receive placebo in the RCP).	The last non-missing valid observation prior to the first administration of IP during RCP.
Day 1	The day of first IP administration and will be denoted by Day 1 (RCP).	The day of first open-label period IP administration and will be denoted by Day 1 (OLP).	The day of first inebilizumab administration irrespective of RCP or OLP and will be denoted by Day 1 (inebilizumab).	The day after the last IP dosing date and will be denoted by Day 1(SFP)
Study day (SDAY) for each period for reporting purpose	For dates prior to Day 1 (RCP): SDAY= Date of Interest – Date of Day 1 (RCP)	For dates prior to Day 1 (OLP): SDAY= Date of Interest – Date of Day 1 (OLP)	For dates prior to Day 1 (inebilizumab); SDAY= Date of Interest – Date of Day 1 (inebilizumab)	SDAY= Date of Interest – Date of Day 1 (SFP) + 1
	For dates on or after Day 1 (RCP) SDAY= Date of Interest – Date of Day 1 (RCP) + 1	For dates on or after Day 1(OLP): SDAY= Date of Interest – Date of Day 1 (OLP) + 1	For dates on or after Day 1(inebilizumab): SDAY= Date of Interest – Date of Day 1 (inebilizumab) + 1	

Table 2 Definition	of Baseline and	Study Day for	Analysis Purnoses
	of Daschine and	Study Day 101	Analysis I ul posts

\*In cases where measurements are taken on the same day as the first administration of IP and no time is reported, it will be assumed that these measurements are taken prior to the first administration of IP.

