Amendment 9.1, 08AUG2023	IgG4-Related Disease

The reason(s) for discontinuing IP must be recorded on the appropriate page of the eCRF. If subjects choose to discontinue IP, the reason, such as an AE, lack of efficacy, or other reason, must be recorded in the eCRF.

Subjects who discontinue IP during the RCP should remain in the study and complete all RCP study visits, assessments, and procedures (with the exception of IP administration and associated

unless they have withdrawn consent for study participation or withdrawn consent for specific assessments (if subjects will not agree to return for visits, safety data can be collected by telephone call if subjects agree).

Subjects who discontinue IP during the RCP may be eligible to enroll in the OLP, if they meet criteria outlined in Section 6.2.3.1. Site Investigators will be trained about the importance of retention of subjects through the completion of the RCP, and patients will be informed about the continued scientific importance of their data even if they discontinue study treatment early.

Subjects who do not participate in the OLP, and subjects who discontinue IP during the OLP, will be asked to return to the clinic for a series of visits occurring every six months for a total of two years after their last dose of IP. These post-discontinuation follow-up visits will include a limited set of assessments including CD20+ B cell counts, immunoglobulins levels, concomitant medications, and adverse events. These visits are described in detail in Section 6.2.4, Safety Follow-Up Period.

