In an optional 3-year OLP, all eligible subjects who choose to participate will receive inebilizumab. Subjects assigned to the placebo group during the RCP will receive 2 inebilizumab infusions (OLP Day 1 and Day 15), while those assigned to the inebilizumab group in the RCP will receive IV inebilizumab on OLP Day 1 and a placebo infusion on Day 15. Both groups will then receive inebilizumab infusions every 6 months for the duration of the OLP. The IXRS will assign the OLP Day 15 treatments, maintaining the blind for the RCP treatments.

In addition, all subjects who discontinue IP during the OLP, or who do not participate in the OLP, will be asked to return to the clinic for a series of follow-up visits with limited assessments, occurring every six months for a total of two years of SFP after their last IP administration. This SFP will provide data on recovery of B cell counts and immunoglobulin levels and monitor for safety events after the IP discontinuation.

A study schematic is presented in Figure 1.

D = day; IV = intravenous.

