#### 3.6.2 Clinical Laboratory Evaluation

Blood and urine samples will be collected for laboratory safety tests at baseline as well as throughout the study. Laboratory toxicities will be defined based on the National Cancer Institute's Common Terminology Criteria for Adverse Events (NCI CTCAE) version 5 for the tests with objective criteria and version 4 for the tests with subjective criteria. The international system of units will be used for all the lab data.

The analysis for the laboratory results is listed in Table 7.

Laboratory dataset	Planned Analysis
Hematology, Chemistry, and Coagulation	• Summary of worst post-baseline toxicity grade
	• Summary of at least 2-grade shift from the baseline to the worst post-baseline toxicity grade
	• Summary of shift from the baseline relative to the normal range
	• Summary of observed values, and changes and percent changes from the baseline
Urinalysis	• Summary of observed values, and changes and percent changes from the baseline
Serum Immunoglobulins	• Summary of observed values, changes and percent changes from the baseline

 Table 7 Laboratory Results Analysis

To evaluate the association between reduced Ig levels and infections/serious infections/opportunistic infections, those AEs will be summarized by the worst Ig Level during the combined RCP and OLP by the categories listed in Table 8.

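### For placebo subjects who cross over, the SFP baseline lies about a year before first inebilizumab and differs from the Combined column, so immunoglobulin decline and recovery are not on one reference

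*SAP*

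**What the plan says.** SAP section 3.1.1 gives a general rule, under which baseline is the last valid value before the first dose of IP, and Table 2 then sets a baseline for each period. The SFP column makes no distinction by arm: "The last non-missing valid observation prior to the first administration of IP during RCP". The Combined RCP and OLP column is tied to the first inebilizumab dose, which it spells out as the "first OLP dose in those randomized to receive placebo in the RCP". The SAP does not explain the difference.

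On the purpose of the period, SAP section 2.2 says: "This SFP will provide data on recovery of B cell counts and immunoglobulin levels and monitor for safety events after the IP discontinuation". Protocol section 6.4.1 describes the visits as a "limited set of assessments including CD20+ B cell counts, immunoglobulins levels, concomitant medications, and adverse events". SAP section 3.1 includes the SFP among the periods for which safety endpoints are summarized. For serum immunoglobulins, Table 7 in section 3.6.2 plans: "Summary of observed values, changes and percent changes from the baseline". Table 7 does not name periods, so its use in the SFP is read from sections 3.1 and 3.6.

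The SFP takes in subjects who never enter the OLP and those who stop IP during it (Protocol section 6.2.4).

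**The concern.** A recovery figure says how far a value has returned towards its level before the drug. The combined tables measure the decline in a crossover subject from just before the first inebilizumab infusion. The SFP tables would measure the return in the same subject from about a year before that infusion. Whatever happened to immunoglobulins in that year is carried into the SFP change.

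The two time points also differ clinically. The RCP baseline comes after 3 to 8 weeks of glucocorticoid, at 20 mg/day prednisone or equivalent (Protocol section 5.1). OLP Day 1 comes after the 8-week taper (section 7.2.1) and the rest of a year on placebo, with flare treatment where it was needed (section 7.6). Protocol section 2.1.1 itself notes that IgG4 falls as patients respond to glucocorticoids, so the two pre-inebilizumab values need not agree.

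Reduced immunoglobulin is an identified risk of inebilizumab (Protocol section 2.1.4), and recovery is a stated reason for having the SFP (section 4.1). A table that blurs recovery weakens what the period was set up to show.

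**Working it through.** **1. Check of the timing inputs against the plan's own figures.** Inputs: screening 28 days, RCP 365 ± 7 days, OLP 1,095 + 10 days, SFP 730 days (Protocol synopsis); OLP Dose 1 falls 1 to 38 days after the Week 52 visit (section 6.2.3.1).

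- Screening, RCP, interval and OLP: 28 + 365 + 38 + 1,095 = 1,526 days, as the synopsis states.
- Maximum participation: 28 + 372 + 38 + 1,105 + 730 = 2,273 days, as the synopsis states.

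**2. Gap from RCP Day 1 to the first inebilizumab dose in a crossover subject.** Gap = (day of Week 52 visit − 1) + interval to OLP Dose 1.

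- Nominal visit: 364 + 1 = 365 to 364 + 38 = 402 days.
- With the ±7-day window: 357 + 1 = 358 to 371 + 38 = 409 days.

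This range is approximate. It counts from Day 1, whereas the baseline value may be earlier. The footnotes to Protocol Table 4 also allow case-by-case timing of OLP doses after a delayed Day 183 dose.

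**3. Who is affected.**

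| Subject | SFP column | Combined column rule | Moved? |
|---|---|---|---|
| Randomized to inebilizumab | before first RCP dose | before first RCP dose | no |
| Placebo, then inebilizumab in OLP | before first RCP dose | before first OLP dose | yes, about a year |
| Placebo, never exposed | before first RCP dose | not applicable | no |

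Only the middle row changes, and only for those who then enter the SFP. About 80 subjects are planned for placebo (100 if enrollment is increased), which is a ceiling. The documents give no estimate of the actual number.

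**4. Effect on the reported change.** Let the OLP Day 1 value be f × the RCP baseline, and the SFP value be r × the OLP Day 1 value. Change since just before inebilizumab is r − 1. Change as Table 2 defines it is r × f − 1. The documents give no value for f; the range 0.8 to 1.2 is an assumption.

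| r | Change from OLP Day 1 | Change from RCP baseline, f = 0.8 | f = 1.0 | f = 1.2 |
|---|---|---|---|---|
| 1.0 | 0% | −20% | 0% | +20% |
| 0.9 | −10% | −28% | −10% | +8% |

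**5. Joining decline and recovery, with assumed IgG values.**

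- RCP baseline 14, OLP Day 1 12, lowest 9, SFP 12 g/L. The combined table gives (9 − 12)/12 = −25%. The SFP table gives (12 − 14)/14 = −14%. Set together, these suggest that less than half of the loss was regained, although the subject is fully back to the pre-inebilizumab level.
- RCP baseline 14, OLP Day 1 16, SFP 14 g/L. The SFP table gives 0%, although the subject is (14 − 16)/16 = −12.5% below the pre-inebilizumab level.

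The distortion can go either way and vanishes at f = 1.

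**The case against.** The strongest reply is that this is a choice and not an error. The RCP baseline of a crossover subject is a genuine pre-inebilizumab value and follows the SAP's general rule. Table 2 sets baselines by period on purpose, so two baselines for one subject are not in themselves a contradiction. A study-entry reference common to everyone in the SFP, including subjects never exposed, can be defended. All of this stands. A reader might infer from the two columns that the SFP reference is simply wrong; the documents do not support that.

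Nor is OLP Day 1 a clean reference. A subject may enter the OLP on glucocorticoid, or as little as 28 days after stopping other immunosuppression (Protocol section 6.2.3.1), and the design assumes that 35% of placebo subjects have a treated flare. The inebilizumab arm's SFP change also contains the effect of the initial steroid taper, so moving the baseline for crossover subjects leaves the two arms' references under different conditions. This stands too. It argues for presenting SFP change by RCP arm and keeping the RCP-baseline version alongside. It does not remove the mismatch between decline and recovery, and the Combined column already accepts the same imbalance.

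The reply is also right on reach. Observed values are shown beside the changes and do not depend on baseline. The planned immunoglobulin and infection summary uses the worst level over the combined RCP and OLP, not SFP change.

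What the reply does not supply is a reason for departing from the Combined column in the period whose purpose is recovery after inebilizumab. The general rule is worded as a default, and Table 2 already leaves it in the OLP and Combined columns.

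**Conclusion.** The point holds in a limited form. For placebo subjects first exposed in the OLP, the SFP immunoglobulin change and percent change run from a value roughly 358 to 409 days before first inebilizumab. They mix a year of unrelated change with recovery, and they cannot be read against the decline in the combined tables. This rests on Table 7 being applied to the SFP, as SAP sections 3.1 and 3.6 indicate.

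The size and direction are unknown. The percentages above come from assumed values and only show that the effect can matter. It is confined to descriptive change columns in an unstated number of subjects. Observed values, any rule based on a fixed threshold, the primary and key secondary analyses, alpha, power and sample size are untouched.

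A reader might extend the point to B cells, since the SFP is meant to show their recovery as well. The public text contains no B-cell change-from-baseline plan and no definition of recovery, so that extension cannot be confirmed. Parts of the SAP are missing from the public copy, and that is not a fault of the plan.

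**What to change.** In the SFP column of SAP Table 2, define baseline for inebilizumab-exposed subjects as the last valid value before their first inebilizumab dose, as the Combined column does. Keep the RCP baseline for placebo subjects who never received inebilizumab. Present SFP change by RCP arm, and retain change from the RCP baseline as a supplementary summary, so that the study-entry view is not lost.

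The cost is one table cell, a sentence on presentation, and one extra set of descriptive tables. The baseline is already defined for the combined analysis and no new data are needed. The drawback is that the two arms' baselines are then taken under different steroid and flare-treatment conditions. The table footnote should say so.

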#### 3.1.2 Analysis Windows

Analysis visit windows will be used for all visit-based assessments to map longitudinal observations to scheduled visits and, thereby, allow for by-visit analyses, since not all assessments are performed on the scheduled day. Unless otherwise specified, all longitudinal efficacy and safety data analyses will be based on the analysis visit windows except the IgG4 RI. The analysis visit windows will be calculated by bisecting the interval between adjacent scheduled visit days, or by  $\pm$  14, 30, or 60 days from the scheduled RCP, OLP, or SFP visit dates, respectively, whichever results in a shorter interval. The IgG4 RI will need the data from lab or image results, which may not be available until several weeks after the scheduled visit. Hence, the IgG4 RI will be summarized by the nominal visit per protocol.

The actual assessment day will be mapped to the windows defined for each scheduled study visit with following rules:

- If more than one assessment falls within a visit window, the closest non-missing assessment to the scheduled day will be used in the analysis.
- If two non-missing assessment actual dates are equidistant from the target day, the later visit will be used in the analysis.
- For retest values of laboratory data, the retest value (the last valid observation assessed on the same visit day) will be chosen.

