6.1.3 Repeating Procedures After Randomization

Abnormal laboratory or ECG results obtained after randomization that, in the Investigator's opinion, represent a clinically significant finding or clinically significant change from baseline should be repeated as soon as possible, preferably within 48 hours. If urgent results are needed, testing can be sent to a local laboratory, but blood for the same tests should be sent to the central laboratory as well.

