#### **3.6.3** Other Safety Evaluations

#### 3.6.3.1 Vital Signs

The observed values, along with the changes from baseline, will be summarized by visit and by treatment for systolic and diastolic blood pressure (mmHg), pulse rate (beats/min), respiratory rate (breaths/min), body temperature (°C), and body weight (kg). Shift analysis of following BMI categories will be performed:

- Underweight (<18.5 kg/m^2)
- Normal weight ( $\geq 18.5 \text{ kg/m}^2 \langle 25 \text{ kg/m}^2 \rangle$ )
- Overweight ( $\geq 25 \text{ kg/m}^2 <30 \text{ kg/m}^2$ )
- Obese ( $\geq 30 \text{ kg/m}^2$ ).

For vital sign assessments collected on the dosing day, the vital sign data will be presented by time points of interest as well. The time points of interest are as follows:

- Pre-dose assessment.
- During dosing: 15 minutes, 45 minutes, 75 minutes after start of infusion.
- After dosing: immediately after infusion, 60 minutes post-infusion.

In addition, a summary of subjects with clinically significant vital signs values (meeting any of following criteria) will also be provided:

- Systolic blood pressure: < 90 mmHg, > 140 mmHg, > 160 mmHg
- Diastolic blood pressure: < 50 mmHg, > 90 mmHg, > 100 mmHg
- Pulse rate: < 60 beats/min, > 100 beats/min
- Respiratory rate: < 12 breaths/min, > 20 breaths/min
- Body temperature: < 36°C, >38°C
- Body weight: decrease of  $\geq$  7% from baseline and increase of  $\geq$  7% from baseline.

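### Read literally, SAP 3.1.2 applies its one-value-per-window rules to the worst-grade, QTc and vital-sign outlier tables, which would then omit some abnormal results

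*SAP*

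**What the plan says.** SAP 3.1.2 introduces the windows "to map longitudinal observations to scheduled visits and, thereby, allow for by-visit analyses", and then sets their scope: unless specified otherwise, "all longitudinal efficacy and safety data analyses will be based on the analysis visit windows except the IgG4 RI". A window runs to the midpoint between adjacent scheduled visits, or 14, 30 or 60 days either side of the visit (randomized, open-label and safety follow-up periods), whichever is shorter.

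Three selection rules follow:

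- With several values in a window, "the closest non-missing assessment to the scheduled day will be used in the analysis".
- If two values are equally distant from the target day, the later one is taken.
- For laboratory data, "the retest value (the last valid observation assessed on the same visit day) will be chosen".

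SAP 3.6.2 (Table 7) plans a "Summary of worst post-baseline toxicity grade", shifts of at least two grades to the worst grade and, in the text after the table, infections by worst immunoglobulin level. SAP 3.6.3.1 plans "a summary of subjects with clinically significant vital signs values", including weight change, and SAP 3.6.3.2 counts subjects above QTc limits. None of these says which post-baseline values are eligible.

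Protocol 6.1.3 says that clinically significant abnormal laboratory or ECG results obtained after randomization "should be repeated as soon as possible, preferably within 48 hours". Footnote b of Protocol Table 5 also foresees unscheduled clinic visits after open-label telephone contacts.

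**The concern.** Taking one value per window, closest to target, is sensible for by-visit means. It is the wrong rule for an extreme: a worst-grade or threshold table exists to find the most abnormal value, and this selection ignores severity. Because abnormal results are the ones that get repeated or lead to unscheduled draws, they are also the ones most likely to meet a competing value or to fall between windows.

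Neutropenia shows what is at stake. Protocol 2.1.4 lists it as an identified risk that was infrequent and mostly transient. In Study 1155 (Protocol 2.1.5.3), counts of 0.5-1.0 x 10^9/L occurred in 2.3% of inebilizumab subjects and 0% on placebo during the randomized period. With 80 subjects per group, 2.3% is 0.023 x 80 = 1.8, or about two subjects. When the expected count is that small, whether one or two transient values are eligible can change how the laboratory grade table reads.

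**Working it through.** The documents give no figure for this point, so there is none to reproduce. The check applies the SAP 3.1.2 rules to the visit days in Protocol Tables 4 and 5.

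**1. Days in no window, randomized period (laboratory tests and vital signs).** Scheduled days are 1, 15, 29, 57, 85, 113, 141, 183, 211, 239, 267, 295, 323 and 365. Visits 28 days apart or closer leave no gap at 14 days either side. Two intervals are 42 days long:
- Day 141 + 14 = 155 and Day 183 - 14 = 169, so Days 156-168 (13 days) are uncovered.
- Day 323 + 14 = 337 and Day 365 - 14 = 351, so Days 338-350 (13 days) are uncovered.

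Total: 26 of 364 days, or 7.1%. No visit made within its protocol window lands there. The exposed results are those from unscheduled assessments, or from an early discontinuation visit that happens to fall in a gap.

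**2. ECG, randomized period.** ECGs are scheduled on Days 1, 183 and 365. If windows are built on ECG visits only, which the SAP does not say, Days 16-168 and 198-350 are uncovered: 153 + 153 = 306 of 364 days, or 84%.

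**3. Open-label years 2-3.** In-clinic visits at Weeks 52, 78, 104, 130 and 156 are Days 365, 547, 729, 911 and 1093. Within each 182-day interval the windows cover 30 days at each end. For the first interval, Days 396-516 are uncovered, which is 121 days.
- In-clinic visits only: 4 x 121 = 484 of 728 days, or 66%.
- Counting telephone contacts (Weeks 61, 87, 113 and 139) as visits: Days 396-397 and 459-516 are uncovered in the first interval, 2 + 58 = 60 days. Then 4 x 60 = 240 of 728 days, or 33%.

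Over the whole open-label period on in-clinic visits, 590 of 1,092 days (54%) are uncovered.

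**4. Repeat on a later day, inside a window.** Let the abnormal value be o days from target and the repeat L days later. The repeat replaces it when |o + L| <= |o|, that is, when o <= -L/2 (ties go to the later value). The table assumes that visits are spread evenly over the whole days of the protocol visit window, and gives the share of abnormal values replaced.

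| Protocol visit window | L = 1 or 2 days | L = 4 days | L = 6 days |
|---|---|---|---|
| ±1 day | 1/3 = 33% | 0/3 | 0/3 |
| ±3 days | 3/7 = 43% | 2/7 = 29% | 1/7 = 14% |
| ±5 days | 5/11 = 45% | 4/11 = 36% | 3/11 = 27% |
| ±7 days | 7/15 = 47% | 6/15 = 40% | 5/15 = 33% |

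In every cell the original abnormal value is kept more often than it is replaced.

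**5. Repeat on the same day.** For laboratory data the last valid value of that day is used, so the first is always replaced. The SAP has no such rule for ECG or vital signs.

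**6. Unscheduled peak inside a window.** It is lost whenever another value in that window is closer to the target day.

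**The case against.** The strongest reply is that the SAP never meant this. SAP 3.1.2 gives by-visit analysis as the purpose of the windows, and a worst post-baseline grade is a per-subject extreme over a period, so the phrase itself can be read as calling for all values. Dosing-day vital signs are also to be shown at several time points, which cannot coexist with a strict one-value rule. This stands in part: the intent is open, and a reader who infers that these tables will certainly drop peaks goes further than the documents do. But the scope sentence covers all longitudinal safety analyses, its only written exception is the IgG4-RD Responder Index, and the sections that define the tables add none. The all-data wording in SAP 3.1 belongs to the treatment-policy and while-on-treatment strategies, which SAP 3.6.1 applies to adverse events.

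Other limits also stand:

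- A reader might infer that retests displace abnormal QTc and vital-sign values. The retest rule covers same-day laboratory data only, and Protocol 6.1.3 covers laboratory and ECG results. QTc and vital signs are exposed only through the closest-value rule and the window gaps.
- Same-day laboratory retests may be uncommon, because safety samples go to a central laboratory and dosing-day results are not back before dosing (Protocol 6.1.1).
- A reader might infer that neutropenia meeting the discontinuation criterion would vanish. Protocol 6.4.1 requires that count to be confirmed on repeat, so the replacing value is also low.
- Clinically important abnormalities are recorded as adverse events, and cytopenia is an event of special interest reported within 24 hours (Protocol 8.4). This partly compensates, although it relies on investigators' judgement, whereas the grade tables are an objective check.
- The open-label percentages concern a period with no control group and say nothing about a difference between randomized arms.

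**Conclusion.** The point holds on a literal reading of SAP 3.1.2, and no other text rules that reading out. Two programmers could produce different worst-grade and outlier tables from this SAP, and the one who follows the scope sentence would produce the lower counts.

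The uncovered-day figures follow from the visit schedule and the window rule. The open-label figure also depends on which visits define the windows (66% on in-clinic visits, 33% with telephone contacts). The 33-47% replacement share rests on evenly spread visits and a repeat after 1-2 days; it falls with longer lags, and would fall further if visits cluster on the target day. None of these is an estimate of the undercount. That cannot be sized, because neither document gives a rate of repeat or unscheduled testing.

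No primary or key secondary efficacy analysis is affected. The change is still worth making: it is nearly free, and the tables concerned are the objective summaries of transient laboratory toxicity.

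**What to change.** Add to SAP 3.1.2 that the window and selection rules apply to by-visit summaries only. State that worst post-baseline grade, shift to worst grade, worst immunoglobulin level, QTc thresholds and vital-sign or weight outliers use every valid post-baseline result in the period, including unscheduled and repeat values and those from local laboratories approved under Protocol 6.3.4. A cross-reference in SAP 3.6.2 and 3.6.3 would keep the table specifications consistent.

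The cost is a sentence or two. If all values were intended from the start, nothing else changes; if not, abnormality counts will be slightly higher.
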